9.6 Efficacy Subgroup Analyses

To evaluate the consistency of the efficacy over demographic and other baseline characteristics, subgroup analysis will be performed for the co-primary endpoints for the subgroups listed in [Table 3](#) below using ITT1.

For subgroup analysis, point estimate and 95% CI for each treatment group as well as point estimate and 95% CI for treatment differences between upadacitinib group and placebo group will be presented. No p-value will be provided. If, for a subgroup factor except age, sex and race ([Table 3](#)), any of the resulting categories has fewer than 10% of the planned study size, subgroup analyses will not be presented for that category.

Table 3. Subgroups for Efficacy Analysis

Subgroup Factor	Categories
Sex	Male, Female
Age	≤ median, > median
Age	≥ 18 years - < 40 years, ≥ 40 years - < 65 years, ≥ 65 years
Race	White, non-White
Race	White, Black or African American, American Indian or Alaska Native, Native Hawaiian or Other Pacific Islander, Asian, Multiple
Baseline fecal calprotectin	≤ 250 µg/g, > 250 µg/g
Baseline CD-related Steroids Use	Yes, No
Baseline CD-related immunosuppressant use	Yes, No
Baseline CD-related aminosalicylate use	Yes, No
Baseline CD-related antibiotic use	Yes, No
Baseline hs-CRP	≤ 5 mg/L, > 5 mg/L
Baseline CDAI	≤ 300, > 300
Baseline very soft/liquid SF	≤ median, > median
Baseline AP score	≤ median, > median
Baseline SES-CD	< 15, ≥ 15
Crohn's Disease Location at Baseline	Colonic only, Ileal only, Ileal-colonic
Body Weight	≤ median, > median
BMI	Underweight [$< 18.5 \text{ kg/m}^2$], Normal [≥ 18.5 and $< 25 \text{ kg/m}^2$], Overweight [≥ 25 and $< 30 \text{ kg/m}^2$], Obese [$\geq 30 \text{ kg/m}^2$]
Disease Duration	≤ 5 years, > 5 years
Geographic Region	North America, Western Europe, South/Central America, Eastern Europe, Asia, Other
Number of Prior Biologics Failed	≤ 1, > 1
Prior TNF Failure	1, > 1
Prior Ustekinumab Failure	Yes or No
Prior Vedolizumab/Natalizumab Failure	Yes or No

10.0 Safety Analyses

10.1 General Considerations

Safety analyses will be performed on the safety population for Part 1 (SA1) and SA-UPA population as defined in Section 4.0. In addition, safety summaries will be performed on the safety analysis set for Part 2 (SA2) and Part 3 (SA3).

The standard safety analyses will include reporting of adverse events (AEs), adverse events of special interest (AESIs), laboratory, and vital signs measurements. Frequency tables and exposure adjusted event rate per 100 patient-years tables of subjects with treatment-emergent adverse events (TEAEs) by system organ class (SOC) and by preferred term (PT) as in the Medical Dictionary for Regulatory Activities (MedDRA) dictionary will be provided by treatment group. All continuous laboratory parameters and vital signs variables at each visit will also be summarized by treatment group. Frequency tables of subjects meeting criteria for potentially clinically important vital sign values and for potentially clinically important laboratory values will be provided by treatment group.

The baseline for safety analysis will be treatment dependent. For the Part 1/Part 2 laboratory and vital signs measurements, the baseline value is defined as the last available measurement before study drug administration for all subjects. Starting from the Part 3, the baseline value for subjects initially randomized to upadacitinib will remain the same. However, the baseline value for subjects initially randomized to placebo will be redefined as the last available measurement before first dose of upadacitinib administration in Part 3.

For the safety analysis, subjects are assigned to a treatment group based on the treatment actually received, regardless of the treatment randomized.

Missing safety data will not be imputed.

10.2 Adverse Events

AEs will be summarized and presented using primary MedDRA SOCs and PTs according to the version of the MedDRA coding dictionary used for the study at the time of database lock. The actual version of the MedDRA coding dictionary used will be noted in the AE tables and in the clinical study report. Specific AEs will be counted once for each subject for calculating percentages, unless stated otherwise. In addition, if the same adverse event occurs multiple times within a subject, the highest severity and level of relationship to investigational product will be reported.

10.2.1 Treatment-Emergent Adverse Events

Part 1 (SA1 population) /Part 2 (SA2 population): TEAEs for Part 1/Part 2 are defined as events that begin either on or after the first dose of the study drug in Part 1/Part 2 and until (i) the first dose of study drug in the Study M14-430 (if applicable), or (ii) until first dose of study drug in Part 3 (if applicable), or (iii) within 30 days after the last dose administration of the study drug in Part 1/Part 2, whichever is earlier.

Part 3 (SA3 population): TEAEs for Part 3 are defined as events that begin either on or after the first dose of the study medication in the Part 3 and until (i) first dose of study drug in the Study M14-430 (if applicable), or (ii) within 30 days after the last dose of the study drug in the Part 3, whichever is earlier.

All Upadacitinib (SA-UPA population): TEAEs for "All Upadacitinib" are defined as events that begin either on or after the first dose of upadacitinib and (i) until first dose of study drug in the Study M14-430 (if applicable), or (ii) within 30 days after the last dose of upadacitinib in the study, whichever is earlier.

24-Week Upadacitinib (SA4 population): TEAEs for "24-Week Upadacitinib" (SA4) are defined as events that begin either on or after the first dose of upadacitinib and until (i) first dose of study drug in the Study M14-430 (if applicable), or (ii) within 30 days after the last dose of upadacitinib in the study, whichever is earlier.

If an incomplete onset date was collected for an adverse event, the event will be assumed to be treatment-emergent unless there is other evidence that confirms that the event was not treatment-emergent (e.g., the event end date was prior to the study drug start date). The number and percentage of subjects experiencing treatment-emergent AEs will be summarized. For Part 1, the risk difference and 95% CI between upadacitinib group and placebo group will be presented.

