4.0 Analysis Populations

The following population sets will be used for the analyses.

Intent-to-Treat (ITT) Populations

The ITT population for the 12-week double blind induction period (Part 1) (denoted by **ITT1**) includes all randomized subjects who received at least one dose of double-blind study drug during Part 1. The ITT1 population will be used for all efficacy and baseline analyses for Part 1.

For ITT1 population, subjects will be included in the analysis according to the treatment groups that they were randomized to.

The ITT population for the 12-week open-label induction period (Part 2) (denoted by **ITT2**) includes all subjects who have received at least one dose of study drug in Part 2. The ITT2 population will be used for all efficacy and baseline analyses for Part 2.

The ITT population 3 (**ITT3**) includes all subjects who have received at least one dose of study drug in the Part 3.

Per-Protocol Population

The Per-Protocol (PP) population represents a subset of the ITT population, consisting of subjects that did not have a major protocol deviation. Major protocol deviations leading to exclusion from the PP population will be identified prior to database lock.

For **PP** population, subjects will be included in the analysis according to the treatment groups that they were randomized to.

Safety Populations

The safety population for Part 1 (denoted by **SA1**) includes all subjects who received at least one dose of the study drug in Part 1.

The safety population for Part 2 (denoted by **SA2**) includes all subjects who received at least one dose of the study drug in Part 2.

The safety population for Part 3 (denoted by **SA3**) includes all subjects who received at least one dose of the study drug in Part 3.

The safety population for subjects who receive upadacitinib in Part 1 or Part 2 and enrolled in Part 3 (denoted by **SA4**) is a subset of SA3 which includes Cohort 2/Cohort 3 of SA3, defined as subjects who received upadacitinib in Part 1 or Part 2 and received at least one dose of study drug in Part 3.

The all upadacitinib safety population (**SA-UPA**) includes all subjects who received at least one dose of upadacitinib in Part 1 or Part 2 or Part 3.

For the safety populations, subjects are assigned to a treatment group based on the "as treated" treatment group, regardless of the treatment randomized. The "as treated" will be determined by the most frequent dose regimen received in the analysis period.

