10.2.4 Treatment-Emergent Adverse Events per Patient-Years of Exposure

TEAEs will be summarized by event rate per 100 subject years, defined as

$$100 \times \frac{\text{Number of TEAEs}}{\text{Total Patient Years}}$$

where total patient years is defined as the sum of the study drug exposure of all subjects, normalized by 365.25, and rounded to 1 decimal place. Note that one event per preferred term per day per subject will be counted in the calculation of the number of AEs (i.e., a preferred term will not be counted twice on the same day for the same subject).

The TEAE rates per 100 patient-years of exposure will be provided for each AE category in the AE overview summary (defined in Section 10.2.2) and for TEAE summary by SOC and PT.

The study drug exposure for each safety population is defined in the table below.

Safety Population	Scenario	Study Drug Exposure Definition
SA1, SA2	Enrolls in Study M14-430 or Part 3 at the end of Part 1/Part 2	Last dose date in Part 1/Part 2 - 1 st dose date in Part 1/Part 2 + 1
	Does not participate in the Study M14-430 or Part 3	
SA3	Enrolls in Study M14-430	Last dose date in Part 3 - 1 st dose date in Part 3 + 1
	Does not participate in the Study M14-430	
SA4	Enrolls in Study M14-430	Last dose date in Study M14-431 - 1 st dose date in Part 1/Part 2 + 1
	Does not participate in the Study M14-430	
SA-UPA	Enrolls in Study M14-430	Last dose date of upadacitinib in Study M14-431 - 1 st dose date in upadacitinib in M14-431 + 1
	Does not participate in the Study M14-430	

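### The 24-week upadacitinib safety set (SA4) counts induction time in which its members could not have died or stopped drug, so those two rates are about half the Part 3 rate

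*SAP*

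**What the plan says.** SAP 4.0 makes SA4 a subset of SA3, consisting of Cohorts 2 and 3: "defined as subjects who received upadacitinib in Part 1 or Part 2 and received at least one dose of study drug in Part 3". Under SAP 10.2.1 its treatment-emergent events start at the first upadacitinib dose, which for these subjects is the first induction dose: "SA4) are defined as events that begin either on or after the first dose of upadacitinib and until (i"). The window closes at the first Study M14-430 dose or "within 30 days after the last dose of upadacitinib in the study, whichever is earlier".

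The exposure table in SAP 10.2.4 gives SA4 the span "Last dose date in Study M14-431 - 1 st dose date in Part 1/Part 2 + 1". SA3 gets Part 3 dosing time only: "Last dose date in Part 3 - 1 st dose date in Part 3 + 1". The rate denominator is set out as follows: "where total patient years is defined as the sum of the study drug exposure of all subjects, normalized by 365.25". SAP 10.2.4 then requires rates for every overview category: "The TEAE rates per 100 patient-years of exposure will be provided for each AE category in the AE overview summary". The overview in SAP 10.2.2 includes events leading to discontinuation of study drug and events leading to death.

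SAP 10.1 names SA1, SA-UPA, SA2 and SA3 as the sets for safety analysis and does not name SA4. The version history (SAP 13.0, version 4.0) records that SA4 and its event definition were added for the safety analysis.

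**The concern.** Whether a subject belongs to SA4 is settled only at the first Part 3 dose, about 12 weeks after the set's clock starts. A subject who dies in induction cannot take that dose. Nor can one who permanently stops study drug: under Protocol 5.1, subjects who stop drug but stay in the study are no longer dispensed any. For these two outcomes the induction days of every SA4 member go into the denominator, although no such event could have fallen in them. This is immortal time.

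SA4 is the set labelled as 24 weeks of upadacitinib, so its table is where a reader would look for tolerability over the longer exposure. For the same subjects and largely the same events, its discontinuation rate would come out at about half of what SA3 Cohorts 2 and 3 imply, with nothing in the table to explain why. The other sets do not share the problem, because none of them has an entry condition that is met after its own clock starts.

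**Working it through.** **Inputs**

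- Induction length T1: 12 weeks × 7 = 84 days (Protocol 5.1, SAP 2.2).
- Scheduled Part 3 length T3: 12 weeks × 7 = 84 days (same sections).
- Visit window: ±3 days (Protocol 5.1).
- Mean Part 3 exposure actually achieved: not given, so a range is assumed.
- Hazards in induction (h1) and Part 3 (h3): not given.

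**The plan's own figure.** T1 + T3 = 84 + 84 = 168 days = 24 weeks, which reproduces the length in the set's label. The documents state no SA4 event rate.

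**Ratio to the rate over time at risk.** Let D be the number of deaths or discontinuations in SA4. All occur after Part 3 entry.

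- SAP rate: D / (T1 + T3)
- Rate over Part 3 time: D / T3
- Ratio: T3 / (T1 + T3)

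| Mean T3 (days) | Ratio with T1 = 84 |
|---|---|
| 84 (full schedule) | 84/168 = 0.50 |
| 60 (assumed) | 60/144 = 0.42 |
| 42 (assumed) | 42/126 = 0.33 |

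Shifting the Week 12 and Week 24 visits by 3 days in opposite directions gives 78/165 = 0.47 and 90/171 = 0.53.

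**Simulation.** Event times were drawn for 2,000,000 subjects at constant hazards of 5, 20 and 50 per 100 patient-years. The SA4 rule returned 2.5, 9.8 and 24.2. Counting everyone from first dose recovered 5.0, 20.0 and 50.0.

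**In patient-years (illustration).** Take 330 upadacitinib subjects from Part 1 and 130 from Part 2, the 52% response rate in SAP 2.4, and assume that every non-responder enters Part 3 with full exposure. Then (330 + 130) × 0.48 ≈ 221 subjects. With an assumed 10 discontinuations:

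- SAP rule: 221 × 168 / 365.25 = 101.7 patient-years; 10/101.7 = 9.8 per 100
- Part 3 time: 221 × 84 / 365.25 = 50.8 patient-years; 10/50.8 = 19.7 per 100

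**Ratio to a 24-week average rate.** With T1 = T3 the SA4 rate is h3/2 and the average is (h1 + h3)/2, so the ratio is 1/(1 + h1/h3):

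- h1 = h3/2: 0.67
- h1 = h3: 0.50
- h1 = 2 × h3: 0.33

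**Against the induction rate.** The SA4 rate h3/2 is below h1 only if h1 exceeds h3/2.

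**The case against.** The strongest case on the other side is that SA4 is a single-arm descriptive subset whose entry condition is openly stated. The unconditional picture is already planned: SA1 and SA2 show induction deaths and discontinuations, SA3 shows Part 3 alone, and SA-UPA covers all upadacitinib exposure. The numbers and percentages of subjects in the overview do not depend on patient-years, and SAP 10.1 does not list SA4. All of this stands, and it confines the problem to one set of rates. It does not make those rates right. SA4 has its own population, event window and exposure row, and the version history says that it was added for the safety analysis.

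Three stronger readings are tempting, and the documents do not support them.

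- A reader might infer that the SA4 rates are at most half the true rate. That follows only against the Part 3 time-at-risk rate. Against a 24-week average it fails whenever the induction hazard is below the Part 3 hazard, which is possible: SAP 2.2 lets Part 3 subjects with persistent symptoms or worsening disease be discontinued at any time. For deaths, the 30 days after last dose count for events but not for exposure, so against the underlying hazard the ratio could reach (84 + 30)/168 = 0.68 in subjects who do not enter Study M14-430. Against a Part 3 rate built by the SAP's own convention it stays at 0.50.
- A reader might infer that SA4 will look safer than both induction and Part 3. Only the comparison with Part 3 is structural.
- A reader might infer that serious, severe and all other events are halved too. Events that do not prevent Part 3 entry can be counted in both periods. Serious and severe events may be depleted in induction to the extent that they ended treatment, but the documents give no basis for a figure.

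Moving the whole event clock to Part 3 would also be a mistake. Events are assigned by onset, so one that begins in induction and stops drug in Part 3 would be lost.

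**Conclusion.** The defect is real and limited to SA4. For events leading to death or to discontinuation of study drug, the rate per 100 patient-years is about half the rate over Part 3 time at risk when Part 3 exposure is complete, and less than that when mean exposure is shorter. The 0.50 rests on the scheduled 84 + 84 days; the 0.42 and 0.33 rest on assumed exposures. How SA4 compares with a 24-week average depends on two unknown hazards, and whether it falls above or below the induction rate is not established. No efficacy result is touched. The change is worth making because the SAP requires these rates and, as written, the rule produces figures that do not measure risk over the time in which the events could occur.

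**What to change.** - **SAP 10.2.4:** for SA4 events leading to death or to discontinuation of study drug, start patient-years at the first Part 3 dose.
- **SAP 10.2.1:** for the same two categories, count an event if the discontinuation or death falls on or after that dose, whatever the onset date, so that events beginning in induction are kept.
- **Other SA4 overview categories:** show them by period (induction; Part 3). Add a footnote that the induction column is conditional on completing induction as a non-responder and entering Part 3.
- **SAP 10.1:** state that SA4 is reported and that SA-UPA is the unconditional summary of all upadacitinib exposure.

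The cost is SAP wording and one more table layout, with no new data. The SA4 rates for the two categories become less favourable, and they will largely overlap with SA3 Cohorts 2 and 3.

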10.2.2 Adverse Event Overview

An overview of AEs will be presented consisting of the number and percentage of subjects experiencing at least one event for each of the following AE categories:

- Any TEAE
- Any TEAE related to COVID-19
- Any TEAE that was rated as related to study drug by the investigator.
- Any severe TEAE
- Any serious TEAE.
- Any TEAE leading to discontinuation of study drug.
- Any TEAE leading to death.
- Treatment-emergent AESI ([Appendix B](#)).
- All deaths
 - Deaths occurring \leq 30 days after last dose of study drug
 - Deaths occurring $>$ 30 days after last dose of study drug
 - Deaths related to COVID-19

In addition, an overview of AEs per 100 patient-years of study exposure will be presented for the AE categories defined above. The number of TEAEs reported, the total number of years of study drug exposure, and the TEAE rate per 100 patient-years will be presented.

10.2.3 Treatment-Emergent Adverse Events by SOC and/or PT

TEAEs will be summarized by SOC and PT; by maximum relationship to study drug as assessed by the investigator (e.g., reasonable possibility or no reasonable possibility) and SOC and PT; by maximum severity and SOC and PT; and by subject number and SOC and PT. Specific AEs will be counted once for each subject for calculating percentages, unless stated otherwise. In addition, if the same AE occurs multiple times within a subject, the highest severity and level of relationship to investigational product will be reported. The SOCs will be presented in alphabetical order, and the PTs will be presented in alphabetical order within each SOC.

For summary by maximum severity, if a subject has an AE with an unknown severity, then the subject will be counted in the severity category of unknown, even if the subject has another occurrence of the same event with a severity present. The only exception is if the subject has another occurrence of the same AE with the most extreme severity – severe. In this case, the subject will be counted under the severe category.

For summary by maximum relationship to study drug, if a subject has an AE with an unknown relationship, then the subject will be counted in the relationship category of "unknown," even if the subject has another occurrence of the same event with a relationship present. The only exception is if the subject has another occurrence of the same AE with a relationship assessment of "Reasonable Possibility." In this case, the subject will be counted under the "Reasonable Possibility" category.

In addition, TEAEs will be summarized by PT and sorted by decreasing frequency for the upadacitinib 45 mg QD treatment group.

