### 6.1.3 Relationship to Study Drug

The investigator will use the following definitions to assess the relationship of the AE to the use of study drug:

- |                                  |   |
|----------------------------------|---|
| Reasonable Possibility    | After consideration of factors including timing of the event, biologic plausibility, clinical judgment, and potential alternative causes, there is sufficient evidence (information) to suggest a causal relationship.   |
| No Reasonable Possibility | After consideration of factors including timing of the event, biologic plausibility, clinical judgment, and potential alternative causes, there is insufficient evidence (information) to suggest a causal relationship. |

For causality assessments, events assessed as having a reasonable possibility of being related to the study drug will be considered "associated." Events assessed as having no reasonable possibility of being related to study drug will be considered "not associated." In addition, when the investigator has not reported causality or deemed it not assessable, AbbVie will consider the event associated.

[figure not shown]
If an investigator's opinion of no reasonable possibility of being related to study drug is given, an "Other" cause of event must be provided by the investigator for the SAE.

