#### **8.1.7 Safety Analyses**

Safety analyses will be performed on safety analysis sets (Part 1, Part 2 and Part 3), as defined in Section 8.1.1.2. Incidence of AEs, changes in vital signs, physical examination results, and clinical laboratory data will be assessed throughout the study. ECGs will be performed at screening and at the end of each Part 1, 2, 3 of the study. AEs and laboratory data when available will be graded as described in the NCI CTCAE, and summarized accordingly.

AEs will be coded using the Medical Dictionary for Regulatory Activities (MedDRA). Treatment-emergent AEs are defined as events that begin or worsen either on or after the first dose of the study drug and within 30 days after the last dose of the study drug for subjects who do not participate in Study M14-430, or within 30 days after the last dose of the study drug in Study M14-431 or first dose of study drug in Study M14-430 if the subject enrolls in Study M14-430, whichever comes first.

An overview of treatment-emergent AEs, including AEs leading to death, AEs leading to premature discontinuation, AEs by MedDRA preferred term and system organ class, AEs by maximum relationship to study drug, AEs by maximum severity and AEs of special interest will be summarized by number and percentage.

Changes from Baseline in continuous laboratory and vital sign parameters will be summarized by treatment group. Treatment group differences between upadacitinib and placebo groups for changes from Baseline may be analyzed using a one-way ANOVA. Vital signs and laboratory data will be described by statistical characteristics and frequency of abnormal values. In addition, shift tables and listings will be provided for abnormal values, whereby the normal range of the analyzing laboratory will be used. Analysis details will be specified in the SAP.

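### TEAEs with missing or not-assessable causality count as drug-associated under Protocol 6.1.3 but drop out of the SAP's related-TEAE overview row and its rate

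*SAP*

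**What the plan says.** **Protocol.** Section 6.1.3 gives the investigator two answers: a reasonable possibility of a causal link (associated) or none (not associated). It then covers the case where there is no usable answer: "when the investigator has not reported causality or deemed it not assessable, AbbVie will consider the event associated". Nothing in the section limits this to expedited reporting. Section 8.1.7 plans a summary of "AEs by maximum relationship to study drug", sets no other causality rule, and leaves analysis details to the SAP.

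**SAP.** Section 10.2.3 tabulates TEAEs "by maximum relationship to study drug as assessed by the investigator". For that table, "if a subject has an AE with an unknown relationship, then the subject will be counted in the relationship category of" *unknown*. It continues: "The only exception is if the subject has another occurrence of the same AE with a relationship assessment of" *Reasonable Possibility*. Another occurrence rated unrelated does not move the subject. The overview in Section 10.2.2 has a row for "Any TEAE that was rated as related to study drug by the investigator" and none for unknown causality; the same categories are also reported as rates per 100 patient-years. Section 10.1 adds: "Missing safety data will not be imputed".

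No SAP text maps missing causality to associated, and the version history in Section 13.0 lists no departure from the protocol on this point.

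**The concern.** The same event can be associated under the protocol and absent from the SAP's headline count of related TEAEs. The sponsor's causality classification and the study tables could then disagree, and the overview would give the reader no sign of it. At stake is the one causality-based row of the overview, with its rate, and to a lesser extent the relationship table by SOC and PT. No efficacy result and no all-causality safety comparison depends on it.

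**Working it through.** The documents state no figure on this point, so there is nothing to reproduce. The check compares the two counting rules table by table.

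**1. Relationship table, per preferred term (SAP 10.2.3).** Let R be subjects with at least one occurrence rated as a reasonable possibility. Let U be subjects with an occurrence of unknown relationship and no such rating.

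- SAP related count: R
- Protocol 6.1.3 count: R + U
- Shortfall: (R + U) − R = U, which is at least 0

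The SAP's unknown category holds exactly these U subjects, so a reader can recover R + U for each term by adding two categories.

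**2. Overview row, subjects (SAP 10.2.2).** Let R* be subjects with any TEAE rated related. Let U* be subjects with none rated related but at least one of unreported or not-assessable causality.

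- SAP count: R*
- Protocol count: R* + U*
- Shortfall: U*, which is at least 0

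The overview does not print U*. Adding the per-term unknowns does not give it, because a subject can be unknown for several terms and rated related for another.

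**3. Overview row, rate (SAP 10.2.2 and 10.2.4).** The rate is 100 × events / patient-years. If E is the number of TEAEs with missing or not-assessable causality, the shortfall is 100 × E / patient-years. This counts events, so it includes events in subjects already in R*. The rate can therefore fall short even when U* = 0.

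**4. Size per subject.** The planned Part 1 arms are 330 upadacitinib and 165 placebo (Protocol 8.3).

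- Upadacitinib: 1/330 = 0.30 percentage points
- Placebo: 1/165 = 0.61 percentage points

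**5. Size per event, as an illustration.** Assume every planned subject takes 12 weeks of drug (84 days).

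- Upadacitinib: 330 × 84 / 365.25 = 75.9 patient-years; 100 / 75.9 = 1.3 per 100 patient-years
- Placebo: 165 × 84 / 365.25 = 37.9 patient-years; 100 / 37.9 = 2.6 per 100 patient-years

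Shorter exposure makes each shift larger.

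**6. Between-arm difference.** The direction is fixed within an arm but not between arms. Moving to the protocol rule changes the difference in related proportions by U*(upadacitinib)/330 − U*(placebo)/165, which can have either sign.

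**7. Rows that do not move.** In SAP 10.2.2, serious TEAEs, TEAEs leading to death, deaths and AESIs are counted without regard to causality. SAP 10.2.5 and 10.2.6 do the same by SOC and PT.

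**The case against.** The best defence is that two assessors are involved. The protocol sentence says how the sponsor will regard the event; the SAP tables are labelled as investigator ratings, and an investigator who gave no rating did not rate the event as related. Protocol 8.1.7 also leaves the detail to the SAP. This explains the SAP wording but does not remove the gap. Section 6.1.3 is the protocol's only rule for unrated events and is not confined to expedited reporting, and the SAP neither states nor explains a departure.

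A second defence is openness. The SOC/PT table shows unknown as its own category and ranks it above unrelated, so nothing is hidden there. That stands for the SOC/PT table but not for the overview, which has no such line.

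A third is that blanks should be rare. The investigator must record a relationship for every AE on a two-option scale (Protocol 6.1 and 6.1.3), and eCRFs are reviewed for completeness (Protocol 10.2). That is fair, and it is why the effect may be nil.

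The no-imputation rule in SAP 10.1 is weaker support. SAP 10.2.1 already takes a cautious default for an AE with an incomplete onset date, treating it as treatment-emergent unless other evidence shows otherwise.

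A reader might also infer that the shortfall falls mainly on deaths and other grave events, or that it alters a related-SAE or related-death row. The documents support neither. They do not say which events lack causality. Serious events are reported within 24 hours, and an unrelated rating for one requires another cause to be named. The SAP overview contains no row for related SAEs or related deaths.

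**Conclusion.** The inconsistency is real but conditional. Within each arm, the SAP's related count and rate can equal or fall below the protocol-rule values and can never exceed them. The effect matters mainly in the overview row and its rate, because the SOC/PT table lets the reader add the unknowns back.

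It would be too strong to say that drug-related events are under-counted outright. That requires missing or not-assessable causality to occur, and the documents give no frequency for it, so any total would be a guess. What can be stated is the effect per subject: 0.30 points on upadacitinib and 0.61 points on placebo at the planned arm sizes.

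Two assumptions underlie this. The SAP's unknown class is taken to be the protocol's unreported or not-assessable class, which is reasonable because the SAP offers no other place for such events. The treated Part 1 arms are taken to be close to the planned 330 and 165.

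**What to change.** In SAP 10.2.2 and 10.2.3, count a TEAE with missing or not-assessable causality as related, following Protocol 6.1.3. Relabel the overview row, for example *related per investigator, or causality missing/not assessable*, so that it does not report ratings no investigator made. Footnote by arm how many subjects were classed this way and, for the rate, how many events. The investigator-only figures can then still be recovered.

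The cost is a change of SAP wording, one derivation rule and a footnote. The downside is that related counts become slightly less favourable if any causality is missing.
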